#### **Secondary Objectives:**

1. Mean and median joint scores in treated vs placebo patients at 16 weeks, compared to baseline scores.
2. Proportion of patients who achieve improvement in SLEDAI 2K at 16 weeks of >3 points, comparing abatacept to placebo.
3. Proportions of patient who do not worsen by PGA score ( $\leq 0.8$  change from initial PGA score on 3 point line).
4. Mean and median changes in CDAI comparing abatacept to controls at 8, 12 and 16 weeks.

5. Changes in a) synovitis, b) tenosynovitis and c) erosions measured by high-energy ultrasound with Doppler flow at zero, and 16 weeks, compared to placebo.
6. Steroid sparing effect of abatacept, measured as ability to taper prednisone to <10mg/day by week 16 comparing abatacept-treated subjects to placebo-treated subjects.
7. Change in fatigue from baseline to 16 weeks as measured by the FACIT fatigue score instrument
8. Change in quality of life comparing baseline to 16 weeks as measured by the SF 36.
9. Safety, measured in standard methods as AE and SAE, including likelihood that the AE/SAE was related to the study biologic.
10. Time to response, measured as joint counts (sum of tender and swollen joints) at zero, 4, 8, 12, and 16 weeks.
11. Change in peripheral blood T cell compartments indicating decline in pro-inflammatory profiles, i.e., we expect decrease in CD4+ effector T cells that make IFNgamma (TH1) and IL-17 (TH17) and increase in ratio of Treg to Teff, as well as decreased function of Thelper and increased functions of Tregs. CD4+CD25+ Foxp3+ and CD8+Foxp3+ will be the definition of regulatory T cells. These will be measured at baseline and 16 weeks
12. Change in anti-DNA and total IgG levels, as well as rise in serum complement levels as disease improves and fewer B cells are activated: measure these at zero, 8 and 16 weeks.
13. Effects of abatacept on serum levels of BLyS (BAFF). As numbers of activated B cells and plasmablasts fall, we expect an increase in BLyS levels. Measure at baseline and 16 weeks.
14. Changes in transcriptome in whole blood and/or purified mononuclear cells in peripheral blood, and changes in interferon-induced gene expressions at baseline that may predict response or non-response at 16 weeks. Measure at baseline and last study visit.

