## **8 STATISTICAL CONSIDERATIONS**

### **8.1 Sample Size Determination**

We based our sample sizes on the preliminary data (unpublished): SLE patients with arthritis at the start of a treatment had a mean score on 66-joint count of  $21 \pm 8.2$ . There was a decrease to a mean of  $2.0 \pm 1.5$  after 12 weeks of various interventions in patients who reported they improved. For the study proposed here, if 67% of abatacept pts will achieve 20% improvement in swollen and tender joints vs. 30% of controls by week 16, n=28 per group (with p=0.05, power=0.8). Thus we plan 32 patients for abatacept over 16 weeks and 32 patients for placebo over 16 weeks, a total of 64. The dropout rate in the abatacept non-nephritis lupus trial was 35% (over 12 months). We anticipate one-third that in a 4 month trial, proposed, here – i.e. 12%. If we begin with 64 patients we should have 56 completers, thus approximately 28 in each group.

Thus, we will plan to recruit 32 SLE patients at UCLA and an additional 32 at UCSD (separate contract).

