### ***8.4.3 Efficacy Analyses***

The Fisher's exact test will be used to compare the percent of subjects achieving primary and secondary outcomes between two groups. Wilcoxon rank sum tests will be used to compare ordinal and quantitative outcomes between groups. Logistic regression will also be used to adjust for baseline clinical presentation and demographic factors. A site by treatment interaction effects will be included in the model to account for possible differences in treatment efficacy between our two sites. Bivariate analysis and nonparametric analysis (for example local polynomial regression or generalized additive model analysis) will be carried out to inspect the relationship between outcome and covariates. The goodness-of-fit of logistic models will be evaluated using the Hosmer-Lemeshow test. With the quantitative outcomes such as joint counts, ultrasound measurements, etc we will use Poisson regression to assess the treatment effect or linear regression for continuous outcomes. Poisson regression is a special case of generalized linear model and robust pseudo likelihood inference will be used in the analysis. We also will use multiple imputation technique to accommodate possible missing data at 12 and 24 weeks due to patients lost to follow up. The imputation model will include all baseline 12 week and 24 week outcomes and covariates to impute the missing outcomes . Analyses will be done with and without imputation.

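### Section 8.4.3 specifies no baseline covariate for the quantitative secondary outcomes and does not say whether the week-16 value or the change is analysed; adjusting for baseline would gain precision at almost no cost

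*Combined protocol and SAP*

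**What the plan says.** Section 8.4.3 (Efficacy Analyses) holds the efficacy plan. For outcomes that are not binary it names two approaches:

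- A two-group test: "Wilcoxon rank sum tests will be used to compare ordinal and quantitative outcomes between groups". This test takes no covariate.
- A model: "we will use Poisson regression to assess the treatment effect or linear regression for continuous outcomes". Joint counts and ultrasound measurements are its examples, and robust inference is planned for the Poisson fit. No covariate is listed.

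Baseline adjustment appears once, for binary outcomes: "Logistic regression will also be used to adjust for baseline clinical presentation and demographic factors". The imputation model in the same section does include baseline outcomes.

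The Secondary Objectives in Section 2 describe CDAI, FACIT and SF-36 as changes, and ultrasound as change in synovitis, tenosynovitis and erosions. Joint scores are worded differently: "Mean and median joint scores in treated vs placebo patients at 16 weeks, compared to baseline scores". Section 8.3 also says that the ultrasound scores are set against baseline. Section 4.1 limits ultrasound to the 32 patients at UCLA.

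No section says whether the variable entering the Wilcoxon test or the regression is the week-16 value or the change, or which of these analyses is the main one.

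**The concern.** Two things are left open that affect the precision of every quantitative secondary result.

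The first is the form of the outcome. For joint scores in particular, the objective can be read as a comparison of week-16 values or of changes, and the two can give different answers from the same data.

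The second is the baseline covariate. In a trial of 64 patients, chance differences at baseline are not small. The difference between arms in a baseline mean has standard error √(2/32) = 0.25 SD with 32 per arm, and √(2/16) = 0.35 SD for ultrasound with about 16 per arm. A baseline difference of d SD shifts the expected week-16 comparison by r·d and the change comparison by (r − 1)·d. With d = 0.25 and r = 0.5, that is 0.125 SD in one direction or the other. A model with the baseline value removes this shift and also reduces residual variance. All the baseline values needed are already on the Baseline Visit list in Section 6.1; CDAI is built from joint counts and the two global assessments, all recorded there.

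**Working it through.** **1. The plan's own figure.** Section 8.1 gives "n=28 per group (with p=0.05, power=0.8" on the basis "if 67% of abatacept pts will achieve 20% improvement in swollen and tender joints vs. 30% of controls by week 16". Two-sided α = 0.05 is assumed, since sidedness is not stated. With p̄ = (0.67 + 0.30)/2 = 0.485 and the pooled-variance formula:

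n = [1.96·√(2·0.485·0.515) + 0.842·√(0.67·0.33 + 0.30·0.70)]² / 0.37² = (1.385 + 0.553)² / 0.1369 ≈ 27.4, rounded up to 28.

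Dropout: 28/(1 − 0.12) ≈ 32 per arm, and 64 × 0.88 = 56.3. Both agree with "Thus we plan 32 patients for abatacept over 16 weeks and 32 patients for placebo over 16 weeks, a total of 64" and "If we begin with 64 patients we should have 56 completers, thus approximately 28 in each group". This calculation concerns the binary primary endpoint. It neither supports nor contradicts the present point, but it supplies the 28 completers per arm used below.

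**2. Relative variance of the treatment effect.** Let r be the correlation of a measure between baseline and week 16, and assume the same SD at both times. In units of the variance from the week-16 value alone:

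- week-16 value: 1
- change score: 2(1 − r)
- week-16 value adjusted for baseline (ANCOVA): 1 − r²

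The ratio of ANCOVA to change is (1 − r²)/[2(1 − r)] = (1 + r)/2. It is below 1 for every r below 1, and 1 − r² is below 1 for every non-zero r. So, apart from the degree of freedom spent, adjustment is never less precise than either alternative.

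**3. Detectable difference.** At 80% power with 28 per arm, the week-16 comparison detects (1.96 + 0.842)·√(2/28) = 0.749 SD. The other two methods multiply this by the square root of their relative variance. The documents give no r, so r = 0.3 to 0.8 is an assumed range.

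| r | Variance: change | Variance: ANCOVA | ANCOVA vs week-16 | ANCOVA vs change | Detectable: week-16 (SD) | Detectable: change (SD) | Detectable: ANCOVA (SD) |
|---|---|---|---|---|---|---|---|
| 0.3 | 1.40 | 0.91 | −9% | −35% | 0.749 | 0.886 | 0.714 |
| 0.5 | 1.00 | 0.75 | −25% | −25% | 0.749 | 0.749 | 0.648 |
| 0.7 | 0.60 | 0.51 | −49% | −15% | 0.749 | 0.580 | 0.535 |
| 0.8 | 0.40 | 0.36 | −64% | −10% | 0.749 | 0.474 | 0.449 |

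A true effect of 0.749 SD has 80% power from the week-16 value. From the change score it has 66%, 80%, 95% and 99% at these four values of r; from ANCOVA, 84%, 90%, 97.5% and 99.7%.

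**4. Ultrasound.** With 32 patients, about 16 per arm before any dropout, the week-16 comparison detects 2.802·√(2/16) = 0.99 SD. At r = 0.5, ANCOVA detects 0.99·√0.75 = 0.86 SD.

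**5. Check against the planned rank test.** Trials were simulated with 28 per arm, baseline 21, SD 8.2 at both times and mean falls of 5% and 32%. Power for Wilcoxon on change against ANCOVA was 56% and 76% at r = 0.3, 71% and 83% at r = 0.5, 89% and 94% at r = 0.7, and 98% and 99% at r = 0.8. The falls and r are assumptions. The 21 and 8.2 come from Section 8.1 but are a 66-joint count, whereas the trial uses 28 joints, so these figures only illustrate the direction.

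**6. Why r cannot be taken from Section 8.1.** Its later figure, 2.0 with SD 1.5, is at 12 weeks, on the 66-joint count, and only in patients who reported improvement.

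**The case against.** The strongest reply is that the plan already uses baseline. CDAI, FACIT, SF-36 and ultrasound are described as changes, joint scores are set against baseline, and imputation uses baseline outcomes. This stands. A reader might infer from the unadjusted test that baseline values are thrown away; the documents do not support that. For most of these outcomes the fair comparator is the change score, against which the gain shrinks as r rises.

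Second, the regression sentence lists no covariates at all, not even site, while the same paragraph adjusts the logistic model for baseline. Reading it as a decision to leave baseline out takes silence for exclusion. This also stands: the gap is in specification.

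Third, the gain may be modest. In the simulation, the protocol's planned response rates of 30% and 67% are best matched at r = 0.7 (30.5% and 67.6%), where ANCOVA gains about 5 points over Wilcoxon on change. An unadjusted t-test gained about 2 to 4 points over Wilcoxon in the same setting, so part of the simulated gain comes from replacing a rank test on normal data rather than from adjustment. Both points are correct. They limit the size of the gain but not its direction, and the variance ratios in the table do not depend on the choice of rank test.

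Fourth, a reader might infer that the Poisson model is unworkable because changes can be negative. Nothing says it would be fitted to changes; Poisson for counts and linear regression for changes can coexist.

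**Conclusion.** The point holds as a gap with an inexpensive improvement. Section 8.4.3 specifies no baseline covariate for the quantitative secondary outcomes and leaves the form of the outcome open. Adjusting for the baseline value would reduce variance by about 9% to 64% against a week-16 comparison and 35% to 10% against a change-score comparison, for r from 0.3 to 0.8.

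This rests on an assumed r, on equal SDs at both times, and on a linear model. For the Poisson model of joint counts the same reasoning applies in direction, but the percentages do not carry over exactly.

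It would be wrong to conclude that the planned analyses are invalid: rank tests and change scores are valid under randomisation. Nor is the primary result affected. The primary endpoint is a response of at least 20% relative to each patient's own baseline count, and logistic adjustment is already planned for it.

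**What to change.** In Section 8.4.3, state that the main analysis of each quantitative secondary outcome models the week-16 value on treatment, the baseline value of the same measure, and site:

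- CDAI, FACIT and SF-36: linear ANCOVA.
- Ultrasound scores: linear ANCOVA without a site term, in the UCLA patients.
- Joint counts: the robust Poisson model already planned, with the log of the baseline count as covariate. Eligibility requires at least three affected joints, so the log is defined unless a count falls to zero by the baseline visit; one sentence should cover that case.

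Report the adjusted difference, or the ratio for joint counts, with its 95% confidence interval. Keep the Wilcoxon test as a sensitivity analysis and state there whether it uses the week-16 value or the change.

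The cost is SAP wording and one model degree of freedom for the baseline term, plus one for site where it is included. No visit, procedure or patient is added.

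### The supportive adjusted logistic model has no covariate list or limit with 27 to 31 expected responders, so if the planned effect is real, ordinary maximum likelihood will overstate its odds ratio

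*Combined protocol and SAP*

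**What the plan says.** Section 8.4.3 (Efficacy Analyses) compares the percentages reaching the binary outcomes with Fisher's exact test. It then adds: "Logistic regression will also be used to adjust for baseline clinical presentation and demographic factors". A site-by-treatment interaction is also to be in the model. Bivariate and nonparametric analyses "will be carried out to inspect the relationship between outcome and covariates". One model check is named: "The goodness-of-fit of logistic models will be evaluated using the Hosmer-Lemeshow test". Analyses are to be run with and without multiple imputation.

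The section names no covariates, sets no maximum, gives no rule for what enters the model, and mentions no penalised or exact fit. Section 8.4.4 (Other Analyses) adds nothing.

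Section 8.1 sets the scale: "if 67% of abatacept pts will achieve 20% improvement in swollen and tender joints vs. 30% of controls by week 16", and "If we begin with 64 patients we should have 56 completers, thus approximately 28 in each group". Section 8.2 says that the 64 enrolled patients are analysed. The synopsis expects 30 completers per group.

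**The concern.** Maximum-likelihood logistic estimates are biased away from an odds ratio of 1 when there are few events per fitted term, and the bias grows as terms are added, even irrelevant ones. This model has three terms before any covariate enters, and the covariate set is open. Section 8.3 alone lists five clinical measures recorded from baseline (SLEDAI 2K, BILAG, joint count, and the patient and physician global assessments). Adding age and sex, for illustration, makes seven.

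At stake is the credibility of the adjusted odds ratio that would be reported beside the primary comparison. Two analysts following the same text could use quite different covariate sets and report quite different odds ratios from the same data.

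**Working it through.** **1. The plan's sample size.** With p1 = 0.67, p2 = 0.30, mean 0.485, two-sided 5% (sidedness is not stated; two-sided reproduces the figure) and 80% power:

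n = [1.960 × √(2 × 0.485 × 0.515) + 0.842 × √(0.67 × 0.33 + 0.30 × 0.70)]² / 0.37² = (1.385 + 0.553)² / 0.1369 = 27.4, so 28 per group.

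With 12% dropout, 56 / 0.88 = 63.6, so 64. Both match Section 8.1.

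**2. Expected responders.**
- 56 completers: 28 × 0.67 + 28 × 0.30 = 27.2 (28.8 non-responders).
- 60 completers (synopsis): 30 × 0.97 = 29.1.
- All 64: 32 × 0.97 = 31.0.

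**3. Planned odds ratio.** (0.67/0.33) / (0.30/0.70) = 4.74.

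**4. Bias by assumed covariate count.** Trials were simulated at 67% against 30%, with maximum likelihood fitting treatment, site, their interaction and k normal covariates unrelated to outcome (1,500 to 3,000 trials per setting). Any shift is therefore due to the fitting alone. Inflation is the median fitted odds ratio relative to 4.74. Fits that did not converge were dropped (about 1-3% in most settings).

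| k (assumed) | Terms | Responders per term, n=56 | Median inflation, n=56 | Median inflation, n=64 |
|---|---|---|---|---|
| 0 | 3 | 9.1 | 12% | 11% |
| 2 | 5 | 5.4 | 21% | 16% |
| 3 | 6 | 4.5 | 28% | 21% |
| 5 | 8 | 3.4 | 36% | 29% |
| 8 | 11 | 2.5 | 62% | 51% |
| 10 | 13 | 2.1 | 87% | 72% |
| 12 | 15 | 1.8 | 117% | 82% |

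Separate runs with half the covariates binary agree to within simulation and design differences. At n=56 the median odds ratios were 6.3 with 4 covariates (6.3/4.74, +33%), 6.4 with 6 (+35%), 7.5 with 8 (+58%), 9.0 with 10 (+90%) and 9.6 with 12 (+103%). At n=64 they were 6.0 with 4 (+27%), 7.9 with 10 (+67%) and 8.7 with 12 (+84%). The highest median in any run with 12 covariates was +138%.

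**5. Sensitivities.**
- Without the interaction, n=56: 14% with 2 covariates, 31% with 5, 68% with 10.
- With prognostic covariates (assumed log odds ratio 0.4 per SD, measured against the conditional odds ratio), n=64: 45% with 5 and 142% with 10, against 29% and 72% for irrelevant ones.
- With a true odds ratio of 1, n=56: 0-2% with 5 or 10 covariates.

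**6. Alternative fit.** Firth penalised likelihood on the same models stayed within about 0-11% of the truth. With treatment, site and two covariates, the median was 4.6 to 4.7 against 4.74.

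**7. Model check.** With the usual ten groups, the Hosmer-Lemeshow test has 56/10 = 5.6 patients per group (6.4 with 64). Having both expected counts at 5 or more needs at least 10 per group.

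**The case against.** The strongest reply is that this is a supportive analysis. The primary endpoint is a proportion, and the named comparison is of percentages by Fisher's exact test. The logistic model is used as well, and the plan never names an odds ratio. All of that stands. A reader might infer that the odds ratio is the plan's only treatment-effect estimate, or that the primary conclusion is at risk. The text supports neither.

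Second, the size is conditional. A reader might infer that the odds ratio will be inflated by some 40% to 120%. That needs roughly 6 to 12 covariates, a number found nowhere in the documents, and small models fall well below it. It also assumes that the planned effect is real. This too stands.

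Third, testing is little affected at modest model sizes. Type I error was 5-6% with up to 8 covariates in one set of runs (5-7% in another), reaching 9% only at 12. Interval coverage was about 94-95% with up to 4 covariates.

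Fourth, inspecting outcome-covariate relations may only mean checking functional form, and the text states no selection rule. If it were used to select (15 candidates screened at p<0.2), about 3 would be kept and the median odds ratio would be 6.0 (6.0/4.74, +27%). Likewise, the plan offers the Hosmer-Lemeshow test for goodness of fit, not as protection against overfitting, so its weakness here is secondary.

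The last argument is that a short covariate list alone would be enough. It removes most of the problem but not all: maximum likelihood with site and two covariates, without the interaction, still gave +14%.

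**Conclusion.** The concern holds as a conditional statement about a supportive estimate. If the planned effect is true, the stated fit overstates the odds ratio even with its minimum three terms, and the open covariate set lets the excess grow. Across all runs with irrelevant covariates, the median inflation is about 10-15% with none, 20-30% with 2-4 (single settings ranged from 16% to 33%), 35-60% with 6-8 and 65-140% with 10-12. Results for 64 patients lie towards the lower end.

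These figures rest on 67% against 30% response, 56 to 64 analysed patients and covariate counts that are assumptions of this check. Prognostic covariates would raise them. With a true odds ratio of 1 the bias is essentially nil. The Fisher comparison and the two observed percentages are unaffected. The change is worth making because it is cheap and the bias is avoidable.

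**What to change.** In Section 8.4.3:

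- State that the logistic models are fitted by Firth penalised likelihood with profile-likelihood confidence intervals.
- Limit the adjusted model to treatment, site and a short list of baseline terms, for example two. Name them before unblinding and do not choose them from their observed relation to the outcome. If the site-by-treatment interaction is wanted, report it from a separate model fitted the same way.
- State that the bivariate and nonparametric inspection is descriptive and does not decide what enters the model.
- Optionally, drop the Hosmer-Lemeshow test, which is uninformative at 5 to 6 patients per group.

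The cost is a few sentences of text. Firth fitting is in standard software, and sample size and conduct do not change. The small downside is that fewer covariates are adjusted for and the reported odds ratio will be smaller.

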SLE patients with 3 or more swollen and tender joints and moderate or severe lupus activity (SLEDAI 2K score 4 or greater) will be eligible for this study. In addition, patients must have current or historical documented positive Antinuclear Antibody (ANA) and/or anti-double stranded deoxyribonucleotide antibody (anti-dsDNA).

The established SLE therapy (as allowed by the study) at study entry will be continued as background therapy. Background therapy should be kept stable throughout the study, although increase in prednisone to not more than 30 mg a day, which much be tapered to  $\leq 10$  mg daily by 8 weeks, will be permitted. Tapering of prednisone dose at any time will be permitted. Dosage increases in antimalarial, or any other non-glucocorticoid immunosuppressives, or introduction of any of these or a biologic agent as a new therapy (not allowed by the protocol) will be regarded as a treatment failure. Subjects requiring prednisone or equivalent doses  $>10$  mg a day at/after the 8 week visit will be regarded as treatment failures.

The US will be performed by a rheumatologist with expertise in musculoskeletal ultrasound and images will be digitally saved. US will be performed at UCLA only, for the 32 patients enrolled there. Each UCLA patient will have ultrasounds performed on the same machine by the same ultrasonographer at baseline and 16 weeks.

18-Joint US Scoring System (bilat wrists, bilat MCPs 2-5, bilat PIPs 2-5)

JOINT	VIEW	Power Doppler Synovitis	B-mode Synovial Hypertrophy	Tendons	Erosions
Wrists	Dorsal Longitudinal Midline (Radio carpal, intercarpal)	X	X		
MCPs (2-5)	Dorsal Orthogonal	X	X		X (MCP 1,2, and 5)
	Volar Longitudinal	X	X	X	
	Dorsal Paratendon	X	X	X	
PIP/IP (2-5)	Volar Longitudinal	X	X	X	

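### The robust Poisson inference planned for joint counts and ultrasound scores names no small-sample correction; in its ordinary form it would be anti-conservative at this trial's size, most of all for the UCLA-only ultrasound

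*Combined protocol and SAP*

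**What the plan says.** Section 8.4.3 (Efficacy Analyses) states: "With the quantitative outcomes such as joint counts, ultrasound measurements, etc we will use Poisson regression to assess the treatment effect", with linear regression as the alternative for continuous outcomes. On inference it adds only that "Poisson regression is a special case of generalized linear model and robust pseudo likelihood inference will be used in the analysis".

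The same section gives the same class of outcomes a second test: "Wilcoxon rank sum tests will be used to compare ordinal and quantitative outcomes between groups". It does not say which of the two governs. Proportions, including the primary endpoint, go elsewhere: "The Fisher's exact test will be used to compare the percent of subjects achieving primary and secondary outcomes between two groups".

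On covariates it says "Logistic regression will also be used to adjust for baseline clinical presentation and demographic factors" and "A site by treatment interaction effects will be included in the model to account for possible differences in treatment efficacy between our two sites". Both sentences are attached to the logistic model. No covariate list is given, and whether the adjustment carries over to the Poisson model is not stated.

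On size, section 8.1 plans 64 patients and expects that "we should have 56 completers, thus approximately 28 in each group". Section 4.1 restricts the imaging: "US will be performed at UCLA only, for the 32 patients enrolled there".

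**The concern.** Robust variance is a sensible response to overdispersed counts. The ordinary sandwich, however, is built from fitted residuals, which are smaller on average than the true errors, so it is biased downward when independent patients are few. Comparing the statistic with 1.96 also ignores that the variance is estimated. Both faults push the same way: intervals too narrow and too many false positives.

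At stake are the rate ratios and intervals for joint counts and, more sharply, for ultrasound synovitis, tenosynovitis and erosions. These are a listed secondary objective measured on half the trial. The Wilcoxon test gives no rate ratio, so any effect estimate with an interval on that scale would come from the Poisson model.

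**Working it through.** **Inputs from the documents.** 64 patients, 1:1; 12% dropout; 28 completers per group (8.1; the synopsis expects 30). Ultrasound in 32 UCLA patients (4.1). Baseline 66-joint count 21 ± 8.2, falling to 2.0 ± 1.5 in patients who reported improvement (8.1; ± read as SD).

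**Assumptions, because the documents are silent.** Two-sided 5%; balanced arms at UCLA; week-16 mean and spread of a whole arm; number of covariates; uncorrected sandwich (HC0) with 1.96.

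**Step 1. The plan's own figures.** For 67% vs 30%, with mean rate 0.485:

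n = [1.96√(2·0.485·0.515) + 0.842√(0.67·0.33 + 0.30·0.70)]² / 0.37² = 27.4, so 28 per group, as stated. Completers: 64 × 0.88 = 56.3, so 28 per arm. Ultrasound: 32/2 = 16 per arm, and 16 × 0.88 = 14.1, so about 14. The documents give no type I error for the Poisson tests to reproduce.

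**Step 2. The mechanism in the simplest model.** With treatment only, the log rate ratio is ln(ȳ₁/ȳ₂) and its HC0 variance is Σ SS/(nȳ)² over the two arms. That divides each sum of squares by n where n − 1 is needed. Comparing with 1.96 is therefore like comparing a properly scaled statistic with 1.96√((n−1)/n). If the arm means behave like means of normal data:

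- 28 per arm: 1.96√(27/28) = 1.925; P(|t₅₄| > 1.925) = 6.0%
- 14 per arm: 1.96√(13/14) = 1.889; P(|t₂₆| > 1.889) = 7.0%

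A long right tail raises these figures. A bounded or two-humped distribution can lower them.

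**Step 3. Simulation under no effect, treatment-only model, HC0 with 1.96.** Poisson-lognormal counts, mean 8, 20,000 runs:

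| Setting | log-SD 0.5 | 0.8 | 1.1 |
|---|---|---|---|
| 28 per arm, unbounded | 6.7% | 7.1% | 8.9% |
| 28 per arm, capped at 28 | 6.2% | 6.4% | 6.7% |
| 28 per arm, capped at 56 | 6.6% | 7.2% | 8.1% |
| 14 per arm, unbounded | 7.8% | 8.8% | 11.5% |

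The caps matter because one 28-joint count cannot exceed 28, nor the tender-plus-swollen sum 56.

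Counts built on section 8.1 (a responder/non-responder mixture, 30-67% responders) gave 5.1-5.9% in one set of runs at 28-32 per arm. In a second set, N 56-64 in total, they gave 5.3-7.2% with no covariate or baseline only. The same mixture at N 28-32 in total gave 6.3-7.5%. Gamma-mixed Poisson scores with shape 1-2 at that size gave 9.6-12.3% unadjusted.

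**Step 4. With covariates or extreme overdispersion.** All patients, shape 1-2, with site, interaction and demographics: 8.1-10.7%; shape 0.5 across models: 8.0-12.2%; section 8.1 mixture with interaction and demographics: 5.9-9.2%. Ultrasound, shape 1-2 across models: 9.3-14.8%; shape 0.5: 12.2-15.8%.

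**Step 5. Alternatives on simulated data.**

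- Wilcoxon: about 3-6%.
- Degrees-of-freedom correction (HC1) with t: about 4-7% for all patients in most settings, up to 9.4%; about 4-11% for ultrasound.
- HC3 with t: about 3-7% for all patients; for ultrasound about 3-7% with covariates, but 4-10% with treatment only. In the lognormal model, unadjusted, it gave 5.1 / 5.9 / 7.1% at 28 per arm and 5.0 / 6.1 / 8.1% at 14 per arm.

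**The case against.** **The plan does not commit to the weak version.** This stands. Robust inference is compatible with HC1, HC3 or a t reference. A reader might infer that the planned tests run at about 7-9% for all patients and 9-14% for ultrasound. The documents do not support that as a statement about the plan. It needs HC0 with 1.96, an unbounded spread that the protocol does not give and, for the top figure, a model with treatment, log baseline and three further covariates fitted to 28 patients, which is specified nowhere. What remains is that the section leaves the choice open, and the ordinary form is the faulty one.

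**The protocol's own joint counts give only a small excess.** This also stands: about 5-7% with at most one covariate. The case is stronger for ultrasound, where the sample is half as large and no score distribution is given. Some ultrasound scores may also go to linear regression.

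**Covariate adjustment makes it worse, and the section favours adjustment.** The first half holds in most of the simulated settings. The second half is a reading of sentences written for the logistic model, so the adjusted figures are conditional.

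**A valid test is already planned.** Wilcoxon covers the same outcomes and holds close to 5%. That limits the damage to hypothesis tests, but it does not repair the Poisson intervals, and the section does not say which result is the main one.

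**HC3 with t is not a complete cure.** Correct for treatment-only models with heavy overdispersion, and the reason for treating the ultrasound p-value separately.

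**Conclusion.** The point holds, conditionally. If the uncorrected sandwich with a normal critical value is used, the nominal 5% Poisson tests were above 5% in every setting examined:

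- **All-patient joint counts, unadjusted:** about 5-7% with counts capped at 28 or built on section 8.1; about 8% at the widest spread when capped at 56; about 9% when unbounded. Up to about 12% with covariates and extreme overdispersion.
- **UCLA-only ultrasound, 14-16 per arm:** about 5-12% unadjusted; up to about 16% with covariates or extreme overdispersion.

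The direction follows from the sample size. The amount rests on the assumed spread, covariate number and variance version, so it should be quoted only as a range. The affected analyses are secondary. Nothing here touches the Fisher test of the primary endpoint or the Wilcoxon tests, and the documents give no ground for extending the concern to them.

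**What to change.** In section 8.4.3:

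1. Specify that all Poisson analyses use a small-sample-corrected robust variance (HC3 or Mancl-DeRouen) with a t reference distribution.
2. For the UCLA-only ultrasound scores, take the p-value from a re-randomisation test of the same Poisson statistic, or from the Wilcoxon test already planned, and keep the corrected Poisson interval for estimation.
3. State whether Poisson or Wilcoxon is the main analysis for each count outcome, and which covariates, if any, enter the Poisson model.

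**Cost.** A few sentences and a software option. In the treatment-only model HC3 multiplies the standard error by n/(n−1), and the t value replaces 1.96. At 28 per arm intervals widen by (28/27) × (2.005/1.96) = 1.06, about 6%. At 14 per arm they widen by (14/13) × (2.056/1.96) = 1.13, about 13%. The re-randomisation test must follow the allocation scheme actually used, so that scheme has to be on record; section 5.2 shows only a heading in the available text.
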